5.1.2 Anti-malarial therapy

Participants in Groups 4 and 6 will receive three rounds of antimalarial drugs - each round starting on the day of vaccination (Day 0) at Study Months 0, 1 and 2. Participants in Group 7 will receive two rounds of antimalarial drugs – each round starting on the day of vaccination (Day 0) at Study months 0 and 2. Each round consists of three daily doses of co-formulated dihydroartemisinin/piperaquine on Day 0, 1, and 2 (i.e. the day of vaccination and each day for 2 days after). Dihydroartemisinin/piperaquine tablets (Guilin Pharmaceutical Company or Sigma Tau Pharmaceuticals) for adult patients each contain 40mg dihydroartemisinin and 320mg piperaquine with a therapeutic dose range between 2–10 mg/kg/day dihydroartemisinin and 16–26 mg/kg/dose piperaquine. In addition each participant will receive a single low dose primaquine on the day of vaccination (Day 0). One single low dose primaquine of approximately 0.25mg/kg (Thai Government Pharmaceutical Organisation) will be administered. This drug regimen has been used in mass drug administrations in more than 10,000 participants which have established that this antimalarial drug regimen is safe and effective.

In the unexpected event that volunteers are found to be infected with malaria during screening, baseline or during follow-up examination they will be treated according to the most up-to-date government guidelines.

5.2 Storage of vaccines and anti-malarial medications

The RTS,S/AS01 vaccines must be stored according to the manufacturer's recommendations at +2°C to +8°C. Any temperature deviation outside the range 0 to 8°C must be reported to the GSK Vaccines as soon as detected. Following an exposure to such a temperature deviation, vaccines will not be used until approval has been given by GSK Vaccines. In case of temperature deviation between 0 and 2°C/32 to 36°F the impacted study vaccines can still be administered, but the site must take adequate actions to go back to the defined range +2 to +8°C/36 to 46°F and avoid re-occurrence of such a temperature deviation.

Study anti-malarial medications must be stored at room temperature below 30 degrees Celsius.

All vaccines and study medications will be stored in a safe and locked place, with no access to unauthorized personnel. Only trained, authorized study staff will have access to the vaccines and study medications. Storage temperatures will be monitored daily, according to SOPs at the investigator's site. In addition, for vaccine storage refrigerator(s), an alarm system and a back-up refrigerator will be available in case of power failure/breakdown. All movements of the study vaccines will be documented and cold boxes, with temperature monitoring, will be used to transfer vaccines to the area where it will be administered. Vaccine and study medication accountability, storage, and handling will be in accordance with local SOPs.

This study will not be blinded; i.e. it is an open-label study.

6 SAFETY REPORTING

6.1 SAFETY

The investigator or site staff is/are responsible for the detection, documentation and reporting of events meeting the criteria and definition of an AE or SAE as provided in this protocol. Each subject will be instructed to contact the investigator immediately should the subject manifest any signs or symptoms they perceive as serious.

REPORTING PROCEDURES FOR SERIOUS AEs

In order to comply with current regulations on serious adverse event reporting to regulatory authorities, the event will be documented accurately and notification deadlines respected.

SAEs will be reported to a safety group (specified members of the study team) and medical monitor immediately (within 24 hours) of the investigators being aware of their occurrence. This safety group includes the Principal Investigator, who acts on behalf of the sponsor for notification of SAEs.

SAEs will also be reported to ethics committees and the regulatory authority, in accordance with reporting requirements and according to required timelines.

6.2 Safety definitions

6.3 Definition of an adverse event

An AE is any untoward medical occurrence in a clinical investigation subject, temporally associated with the use of a medicinal product, whether or not considered related to the medicinal product. An AE can therefore be any unfavourable and unintended sign (including an abnormal laboratory finding), symptom, or disease (new or exacerbated) temporally associated with the use of a medicinal product. For marketed medicinal products, this also includes failure to produce expected benefits (i.e. lack of efficacy), abuse or misuse.

Examples of an AE include:

- Significant or unexpected worsening or exacerbation of the condition/indication under study.
- Exacerbation of a chronic or intermittent pre-existing condition including either an increase in frequency and/or intensity of the condition.
- New conditions detected or diagnosed after investigational vaccines administration even though they may have been present prior to the start of the study.
- Signs, symptoms, or the clinical sequelae of a suspected interaction.
- Signs, symptoms, or the clinical sequelae of a suspected overdose of either investigational vaccines/ antimalarial medications or a concurrent medication (overdose per se should not be reported as an AE/SAE).
- Signs, symptoms temporally associated with vaccines/antimalarial drug administration.

- Pre- or post-treatment events that occur as a result of protocol-mandated procedures (i.e. invasive procedures, modification of subject's previous therapeutic regimen).

Examples of an AE DO NOT include:

- Medical or surgical procedures (e.g. endoscopy, appendectomy); the condition that leads to the procedure is an AE/SAE.
- Situations where an untoward medical occurrence did not occur (e.g. social and/or convenience admission to a hospital, admission for routine examination).
- Anticipated day-to-day fluctuations of pre-existing disease(s) or condition(s) present or detected at the start of the study that do not worsen.
- Pre-existing conditions or signs and/or symptoms present in a subject prior to the first study vaccination. These events will be recorded in the medical history section of the CRF.

6.4 Definition of a serious adverse event

A SAE is any untoward medical occurrence that:

- a. Results in death,
- b. Is life-threatening,

Note: The term 'life-threatening' in the definition of 'serious' refers to an event in which the subject was at risk of death at the time of the event. It does not refer to an event, which hypothetically might have caused death, had it been more severe.

- c. Requires hospitalization or prolongation of existing hospitalization,

Note: In general, hospitalization signifies that the subject has been admitted at the hospital or emergency ward for observation and/or treatment that would not have been appropriate in the physician's office or in an out-patient setting. Complications that occur during hospitalization are also considered AEs. If a complication prolongs hospitalization or fulfils any other serious criteria, the event will also be considered serious. When in doubt as to whether 'hospitalization' occurred or was necessary, the AE should be considered serious.

Hospitalization for elective treatment of a pre-existing condition (known or diagnosed prior to informed consent signature) that did not worsen from baseline is NOT considered an AE.

- d. Results in disability/incapacity, OR

Note: The term disability means a substantial disruption of a person's ability to conduct normal life functions. This definition is not intended to include experiences of relatively minor medical significance such as uncomplicated headache, nausea, vomiting, diarrhoea, influenza like illness, and accidental trauma (e.g. sprained ankle) which may interfere or prevent everyday life functions but do not constitute a substantial disruption.

- e. Is a congenital anomaly/birth defect in the offspring of a study subject.
- f. Spontaneous pregnancy loss

- g. Medical or scientific judgment should be exercised in deciding whether reporting is appropriate in other situations, such as important medical events that may not be immediately life-threatening or result in death or hospitalization but may jeopardize the subject or may require medical or surgical intervention to prevent one of the other outcomes listed in the above definition. These should also be considered serious. Examples of such events are invasive or malignant cancers, intensive treatment in an emergency room or at home for allergic bronchospasm, blood dyscrasias or convulsions that do not result in hospitalization.

6.5 *Solicited adverse events*

6.6 *Solicited local (injection-site) adverse events*

The following local (injection-site) AEs will be solicited:

All age groups
Pain at injection site Redness at injection site Swelling at injection site

6.7 *Solicited general adverse events*

The following general AEs will be solicited:

Adult
Fatigue Fever Gastrointestinal symptoms † Headache

† Gastrointestinal symptoms include nausea, vomiting, diarrhoea and/or abdominal pain.

Note: Temperature will be recorded in the evening. Should additional temperature measurements be performed at other times of day, the highest temperature will be recorded in the CRF.

6.8 *Clinical laboratory parameters and other abnormal assessments qualifying as adverse events or serious adverse events*

In absence of diagnosis, abnormal laboratory findings (e.g. clinical chemistry, haematology, urinalysis) or other abnormal assessments that are judged by the investigator to be clinically significant will be recorded as AE or SAE if they meet the definition of an AE or SAE. Clinically significant abnormal laboratory findings or other abnormal assessments that are present at baseline and significantly worsen following the start of the study will also be reported as AEs or SAEs.

The investigator will exercise his or her medical and scientific judgment in deciding whether an abnormal laboratory finding or other abnormal assessment is clinically significant.

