6.18 Assessment of intensity

The intensity of the following solicited AEs will be assessed as described:

Intensity scales for solicited symptoms in adults

Adults		
Adverse Event	Intensity grade	Parameter
Pain at injection site	0	None
	1	Mild: Any pain neither interfering with nor preventing normal every day activities.
	2	Moderate: Painful when limb is moved and interferes with every day activities.
	3	Severe: Significant pain at rest. Prevents normal every day activities.
Redness at injection site		Record greatest surface diameter in mm
Swelling at injection site		Record greatest surface diameter in mm
Fever*		Record temperature in °C/°F
Headache	0	Normal
	1	Mild: Headache that is easily tolerated
	2	Moderate: Headache that interferes with normal activity
	3	Severe: Headache that prevents normal activity
Fatigue	0	Normal
	1	Mild: Fatigue that is easily tolerated
	2	Moderate: Fatigue that interferes with normal activity
	3	Severe: Fatigue that prevents normal activity
Gastrointestinal symptoms (nausea, vomiting, diarrhoea and/or abdominal pain)	0	Normal
	1	Mild: Gastrointestinal symptoms that are easily tolerated
	2	Moderate: Gastrointestinal symptoms that interfere with normal activity
	3	Severe: Gastrointestinal symptoms that prevent normal activity

*Fever is defined as temperature $\geq 37.5^{\circ}\text{C}$ / 99.5°F for oral, axillary or tympanic route, or $\geq 38.0^{\circ}\text{C}$ / 100.4°F for rectal route. The preferred route for recording temperature in this study will be oral.

The maximum intensity of local injection site redness and swelling will be scored as follows:

0	:	0 mm
1	:	> 0 to \leq 50 mm
2	:	> 50 mm to \leq 100 mm
3	:	> 100 mm

The maximum intensity of fever will be scored as follows:

0	:	< 37.5°C (< 99.5°F)
1	:	$\geq 37.5^{\circ}\text{C}$ ($\geq 99.5^{\circ}\text{F}$) to $\leq 38.0^{\circ}\text{C}$ (100.4°F)
2	:	> 38.0°C (> 100.4°F) to $\leq 39.0^{\circ}\text{C}$ (102.1°F)
3	:	> 39.0°C (102.1°F)

The investigator will assess the maximum intensity that occurred over the duration of the event for all unsolicited AEs (including SAEs) recorded during the study. The assessment will be based on the investigator's clinical judgment.

The intensity should be assigned to one of the following categories:

- 1 (mild) = An AE which is easily tolerated by the subject, causing minimal discomfort and not interfering with everyday activities.

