6.22 Analysis of safety

The percentage of subjects with at least one local AEs with at least one general AE (solicited and unsolicited) and with any AE during the 7-day or total follow-up period up to 29 days after the last vaccine dose and overall will be tabulated with exact 95% CI. The percentage of doses followed by at least one local AE (solicited and unsolicited), by at least one general AE (solicited and unsolicited) and by any AE during the 7-day or the total follow up period up to 29days after the last vaccine will be tabulated with exact 95% CI. The same computations will be done for Grade 3 AEs, for any AEs considered related to vaccination and for any Grade 3 AEs considered related to vaccination.

The percentage of subjects reporting each individual solicited local AE (any grade and Grade 3) and solicited general AE (any grade, Grade 3, any related, Grade 3 related, resulting in medically attended visit) during the 7-day follow-up period (Day 0-6) after each vaccine dose and overall will be tabulated for each group. Similarly, the percentage of doses followed by each individual solicited local and general AE will be tabulated, overall vaccination course, with exact 95% CI.

For fever, the number and percentage of subjects reporting fever by half degree (°C) cumulative increments during the first seven days (Day 0-6) after each vaccine dose and overall will be tabulated. Similar tabulations will be performed for any fever with a causal relationship to vaccination and Grade 3 (> 39.5°C) causally related fever.

The percentage of subjects reporting unsolicited AEs from the date of the first vaccine dose up to 29 days after the last vaccine dose and after the sporozoite challenge will be tabulated by group and by MedDRA preferred term with exact 95% CI. Similar tabulation will be done for Grade 3 unsolicited AEs, for any causally related unsolicited AEs and for Grade 3 causally related unsolicited AEs.

The percentage of subjects reporting SAEs and pregnancies will be described in detail.

The percentage of vaccinated subjects reporting AEs of specific interest (meningitis and pIMDs) will be described in detail.

Biochemistry (ALT, AST and creatinine) and haematological (haemoglobin, WBC and platelets) laboratory values will be presented according to toxicity grading scales and tabulated by group.

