15 APPENDIX A: SUMMARY OF STUDY ARMS AND PROCEDURES

Month	Group 1 (n=20) $R_B R_B r_B$	Group 2 (n=20) $2xR_E 2xR_E 2xr_E$	Group 3 (n=30) $R_E R_E R_E$	Group 4 (n=30) $R_E R_E R_E + \text{DHA-PIP} + \text{PQ}$	Group 5 (n=30) $R_E R_E r_E$	Group 6 (n=30) $R_E R_E r_E + \text{DHA-PIP} + \text{PQ}$	Group 7 (n=30) $R_E r_E + \text{DHA-PIP} + \text{PQ}$
0	RTS,S/AS01B Standard dose (0.5mL)	RTS,S/AS01E Double Standard dose (1.0mL)	RTS,S/AS01E Standard dose (0.5mL)	RTS,S/AS01E Standard dose (0.5mL) + DHA-PIP+PQ	RTS,S/AS01E Standard dose (0.5mL)	RTS,S/AS01E Standard dose (0.5mL) + DHA-PIP+PQ	RTS,S/AS01E Standard dose (0.5mL) + DHA-PIP+PQ
1	RTS,S/AS01B Standard dose (0.5mL)	RTS,S/AS01E Double Standard dose (1.0mL)	RTS,S/AS01E Standard dose (0.5mL)	RTS,S/AS01E Standard dose (0.5mL) + DHA-PIP+PQ	RTS,S/AS01E Standard dose (0.5mL)	RTS,S/AS01E Standard dose (0.5mL) + DHA-PIP+PQ	No intervention in M1
2	RTS,S/AS01B 1/5 Standard dose (0.1mL)	RTS,S/AS01E Double 1/5 Standard dose (0.2mL)	RTS,S/AS01E Standard dose (0.5mL)	RTS,S/AS01E Standard dose (0.5mL) + DHA-PIP+PQ	RTS,S/AS01E 1/5 Standard dose (0.1mL)	RTS,S/AS01E 1/5 Standard dose (0.1mL) + DHA-PIP+PQ	RTS,S/AS01E 1/5 Standard dose (0.1mL) + DHA-PIP+PQ

R_B = Standard dose RTS,S/AS01B: 50µg RTS,S + standard dose AS01B (0.5ml containing 50µg MPL + 50µg QS21)

R_E = Standard dose RTS,S/AS01E: 25µg RTS,S + standard dose AS01E (0.5ml containing 25µg MPL + 25µg QS21)

r_B = Fractional dose RTS,S/AS01B (1/5th dose): 10µg RTS,S + 1/5 standard dose AS01B (0.1ml containing 10µg MPL + 10µg QS21)

r_E = Fractional dose RTS,S/AS01E (1/5th dose): 2.5µg RTS,S + 1/5 standard dose AS01E (0.1ml containing 2.5µg MPL + 2.5µg QS21)

2x = Double dose of R_E (i.e. 1.0ml) or r_E (i.e. 0.2ml), as indicated.

DHA-PIP = Dihydroartemisinin/piperazine (for 3 days; day of vaccination and two subsequent days)

PQ = Primaquine (single low dose on day of vaccination)

Study procedures

Month	Scr	M0				M1				M2				M3	M6 ^a	
Day of month		0 ^f	1 ^b	2 ^b	7	0	1 ^b	2 ^b	7	0	1 ^b	2 ^b	7	0	0	
Informed Consent	x															
Inclusion / Exclusion criteria	x	x														
Vaccination		x				x*				x						
DHA/piperazine**		x	x ^b	x ^b		x*	x ^b	x ^b		x	x ^b	x ^b				
PQ single low dose primaquine**		x				x*				x						
History of fever, current axillary temperature***	x	x	x ^b	x ^b	x	x	x ^b	x ^b	x	x	x ^b	x ^b	x	x	x	
Full medical history, vital signs, physical examination	x	x				x				x						

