Ask about any concomitant medication	x	x	x ^b	x ^b	x	x	x ^b	x ^b	x	x	x ^b	x ^b	x	x	x	
Assessment of any adverse event(s)		x	x ^b	x ^b	x	x	x ^b	x ^b	x	x	x ^b	x ^b	x	x	x	
Assess for any withdrawal criteria		x	x ^b	x ^b	x	x	x ^b	x ^b	x	x	x ^b	x ^b	x	x	x	
Blood sample (mL)	Parasite microscopy****					0.5				0.5					0.5	
	Haematology Hb, WBC, PLT	2	2		2				2				2	2		
	Biochemistry ALT, AST, CREA	3	3		3				3				3	3		
	HBsAg, HCV, HIV	1														
	Immunology panel ^c		10			10				10				10	10	
	Piperazine & Primaquine levels*****		1 ^g	1 ^e	1 ^d	1 ^d	1 ^d	1 ^e	1 ^d	1 ^d	1 ^d	1 ^e	1 ^d			
	Blood volume per visit (mL)	6	16	1	1	6	11.5	1	1	6	11.5	1	1	6	15	10.5
	Maximum cumulative blood volume (mL)															94.5
Electrocardiogram (ECG)	x															
Urine pregnancy test	x	x				X				x						

* Procedures are not applicable for study group 7

** Only for study groups 4, 6 and 7, where applicable

*** Axillary temperature will be record from D0-D7 after each vaccination

a) first day of M6

b) Visits on days 1 and 2 post-vaccination are only applicable for study groups 4, 6, and 7 in Months 0 and 2, and for study groups 4 and 6 in Month 1.

c) the immunology panel consists of six assays to be processed at WRAIR:

**** Parasite microscopy for purposes of indicating whether volunteer has been exposed, and not as an assessment of protection.
 
***** Piperaquine and Primaquine levels for group 4 and 6 only. Additional drug level assessment for Primaquine will be done if additional data are required.
	
 • Plasmodium falciparum. Circumsporozoite Protein. (NANP)6 Ab.IgG • Plasmodium falciparum. Circumsporozoite Protein. (NANP)6 Ab.IgG Avidity • Plasmodium falciparum. anti-C-Term Circumsporozoite Ab.IgG • Plasmodium falciparum. anti-C-Term Circumsporozoite Ab.IgG avidity • Plasmodium falciparum. Circumsporozoite Full length (N+C-Terminal) • P falciparum. anti-full length CSP Ab.IgG avidity 
d) Drug level only for Piperaquine
 
e) Drug level for Piperaquine and Primaquine
 
f) If interval between screening and M0D0 is 3 days or less, screening lab results (haematology, biochemistry, parasite microscopy, and urine pregnancy test) can be used for enrolment (M0D0)
 
g) Drug level for Piperaquine and/or Primaquine will be assessed if additional data are required

---	---

Summary of participant visits

Group	Number of visit	Visit timepoints														

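### Fever is ascertained unequally: the antimalarial arms have extra Day 1 and Day 2 clinic temperatures, the day's highest reading is the one recorded, and the measurement route is contradictory

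*Protocol*

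**What the plan says.** **Number of readings.** Section 6.7 sets the routine measurement for every group: "Temperature will be recorded in the evening". It then adds a rule for days with more than one reading: "Should additional temperature measurements be performed at other times of day, the highest temperature will be recorded in the CRF".

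**Who has extra readings.** Appendix A (Study procedures) lists "History of fever, current axillary temperature" at Days 0, 1, 2 and 7 of each round. Footnote b limits two of those days: "Visits on days 1 and 2 post-vaccination are only applicable for study groups 4, 6, and 7 in Months 0 and 2", and to Groups 4 and 6 in Month 1. Groups 1, 2, 3 and 5 have no Day 1 or Day 2 visit.

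**Route.** Section 4.8.4 gives each participant an oral thermometer and a diary card, and section 6.18 states "The preferred route for recording temperature in this study will be oral". Appendix A names the axillary route in the visit row, and its footnote *** says "Axillary temperature will be record from D0-D7 after each vaccination", with no restriction by group. Section 6.18 uses one fever threshold, 37.5°C, for oral and axillary readings.

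**Analysis.** Section 6.22 tabulates fever "during the first seven days (Day 0-6) after each vaccine dose" and solicited events by group. It makes no provision for the unequal number of contacts.

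**The concern.** Groups 3 and 4 have the same vaccine schedule and differ only by the antimalarials; so do Groups 5 and 6. Readers will set their fever columns side by side. Each extra reading under a highest-of-the-day rule is one more chance to reach 37.5°C, and the extra readings exist only in the drug arms.

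The background (section 2) says RTS,S has not been combined with antimalarials before, and that safety of the combination must be confirmed before roll-out. Section 4.7.3 does not list fever among the main side effects of DHA-PIP. A fever excess in Groups 4 and 6 could therefore be read as a vaccine-drug interaction when part of it comes from measuring more often.

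This is more than detail left to an analysis plan, because section 6.7 is a data-recording rule. If the CRF holds only the day's maximum, without source or route, the evening reading may not be recoverable at analysis.

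**Working it through.** **1. Reproduce the visit counts.** The schedule has 9 visits common to all groups: screening, Days 0 and 7 of three rounds, Month 3 and Month 6. Groups 4 and 6: 9 + 2 × 3 = 15. Group 7: 9 + 2 × 2 = 13. These match the 9, 15 and 13 in Appendix A.

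**2. Readings per dose in Day 0-6.** Evening readings: 7 in every group. Day 1 and Day 2 clinic readings: 2 in Groups 4, 6 and 7, none elsewhere. So 7 against 9. Over three doses this is 3 × 7 = 21 against 3 × 9 = 27; for Group 7's two doses it is 2 × 9 = 18, where evening readings alone would give 14. Group 7 lacks Day 1/Day 2 visits in Month 1, but it receives no vaccine then. The Day 0 clinic reading is common to all groups and creates no difference.

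**3. Direction.** Let E0…E6 be the evening readings and C1, C2 the clinic readings.

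- Evening only: P(max(E0…E6) ≥ 37.5)
- Clinic included: P(max(E0…E6, C1, C2) ≥ 37.5)

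The difference is the probability that a clinic reading reaches 37.5°C when no evening reading does. It cannot be negative.

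**4. Size.** The protocol gives no temperature distribution, so everything here is assumed. There is no true drug effect.

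*Model A.* Each reading = mean + post-vaccination rise on Days 1-2 + person effect + reading error. The person and reading SDs are equal. Per-dose fever, evening only against clinic included:

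| Mean, SDs, rise (°C) | Routes at same level | Axillary 0.3°C lower |
|---|---|---|
| 36.8, 0.25, 0.3 | 24.1% v 33.3% | 24.2% v 25.2% |
| 37.0, 0.30, 0.3 | 54.6% v 64.8% | 54.6% v 56.8% |
| 36.8, 0.25, 0 | 10.9% v 12.9% | 11.1% v 11.2% |
| 37.0, 0.30, 0 | 39.3% v 43.6% | 39.2% v 39.7% |

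Differences of 0.1-0.2 points between the evening-only figures in a row are simulation error. With axillary 0.5°C lower, the excess is 0.5 points or less in every row. With routes level but a correlation of 0.8 between the errors of two same-day readings, the first two rows become 24.2% v 28.8% and 54.6% v 59.6%, about half the excess.

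*Model B.* Daily fever probabilities are set so that evening-only fever is about 13% or 33% per dose. Temperature SD is 0.5°C and between-day correlation is 0.3. Excess in percentage points:

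| Same-day correlation | Axillary offset | Base 13% | Base 33% |
|---|---|---|---|
| 0.5 | 0 | 4.6 | 11.0 |
| 0.8 | 0 | 3.0 | 6.7 |
| 0.95 | 0 | 1.4 | 3.2 |
| 0.5 | -0.3°C | 0.9 | 3.2 |
| 0.8 | -0.3°C | 0.3 | 1.0 |
| 0.8 | -0.5°C | 0.1 | 0.2 |

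At zero same-day correlation and no offset the excess would be 6.0 and 16.1 points. That treats two readings in one person on one day as unrelated, so it is an outer bound and not a plausible case.

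**5. In participants.** With 30 per group, the first row of Model A gives 30 × 0.241 = 7.2 against 30 × 0.333 = 10.0 with fever after a dose, about 3 more from measurement alone.

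**The case against.** The case against giving this weight is strong in several respects.

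- *The size may be nil.* If axillary readings run below oral ones, the clinic reading rarely sets the day's maximum. This stands, and it means that mixed routes do not in themselves inflate fever. The offset is not in the documents, so the low end is no better established than the high end.
- *No primary result is touched.* Section 4.2 defines the primary safety outcome by SAEs, the drug against no-drug objective in section 3 is serologic, and section 6.22 plans tabulations with no between-arm fever test. All of this stands.
- *The rule may be meant for home readings only.* Section 6.7 does not say so; as worded it covers any additional measurement.

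A reader might also infer more than the documents support:

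- *That adverse event rates in general are inflated.* The highest-reading rule concerns temperature only. Every group has the same diary and a Day 7 visit, and the question in section 6.17 covers the time since the previous visit. Extra active questioning on Days 1 and 2 in an open-label trial might add reports, but no size can be given and true drug side effects would be mixed in.
- *That the individual holding rule is distorted.* Section 7.2 requires a Grade 3 systemic event persisting for more than 2 consecutive days. Extra readings on Days 1 and 2 cannot alone supply that.
- *That recording D0-D7 contradicts analysing Day 0-6.* Collecting one day more than is analysed, in every group, is not a contradiction.

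**Conclusion.** The point holds as unequal ascertainment of fever with a known direction and an unknown size. Counting the scheduled clinic readings under the section 6.7 rule gives 9 readings per dose in Groups 4, 6 and 7 against 7 elsewhere, so any bias raises fever in the antimalarial arms. Under the assumptions shown it runs from about nil (axillary 0.3-0.5°C below oral, especially with high same-day correlation) to about 10 percentage points per dose (routes level, moderate same-day correlation). That inflation will occur is not shown; that it can occur is.

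The contradiction over oral and axillary route stands on the text alone. It also matters for the size, since the route largely decides which end of the range applies. The consequence is confined to the descriptive reactogenicity tables. This is a cheap improvement, not a threat to the trial's main conclusions.

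**What to change.** 1. Record the evening diary reading and any clinic reading in separate CRF fields, each with route and time, in place of a single daily maximum.
2. Base the between-group solicited-fever table on the evening diary reading for Day 0-6, which all groups share. Each group then has 7 readings per dose, and the difference due to unequal numbers of readings is removed by construction.
3. Tabulate fever including clinic readings separately, so that no fever is lost from safety reporting.
4. Reconcile sections 4.8.4, 6.7 and 6.18 with the Appendix A visit row and footnote *** on the route of measurement.

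The cost is CRF and analysis wording, since diaries are already issued in every group. The small downside is that a daytime fever seen only in clinic appears in the separate table and not in the between-group comparison.
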